4. Patients with strength training will activate type II macrophages which are anti-inflammatory and pro-regenerative, tipping the balance away from inflammation towards regeneration when compared to the other treatment groups. Since strength training is likely to initiate signals of muscle regeneration, and since type II macrophages play a key role in this effect, it is possible that increasing the signaling to the muscle for regeneration may also increase the proportion of active type II macrophages which are anti-inflammatory. To test this hypothesis, we will test the proportion of peripheral blood M1/M2 macrophages at baseline, 6 months and 12 months after the initiation of the intervention. Recognizing that immunosuppression may significantly confound this proportion and overall suppress it, we will also test circulating levels of pro-inflammatory cytokines such as C-reactive protein(CRP), IL-6, IL-1, TNF-alpha, homocysteine, adiponectin, leptin, and resistin as well as pro-regenerative cytokines such as TGF-beta and IL-10.

5. We expect patients with strength training will experience less renal dysfunction, decreased hemoglobin A1C, increased peripheral vascular function, decreased fasting blood sugar when compared to the other treatment groups. The rationale for this hypothesis is the finding that muscle mass provides active regulation of glucose and other metabolites. Therefore increasing this may provide improved metabolic function. These laboratory panels are part of the standard transplant follow-up labs and add no cost to the project.

6. Patients with strength training will have an overall improved sense of well-being and energy level compared to those with physical therapy or no treatment. With twice weekly counseling for activity and nutrition, patients will be asked about their general health, mental health and pain intensity using the PROMIS questionnaires.

METHODS

Setting: The study will include 225 patients, to achieve a goal of 180 patients in the GH study group and 45 patients in the control group. Every patient will be followed for 3 years after the start of the intervention. Patients will start the intervention at least 2 months post-transplant; however they can be enrolled prior to transplant.

Main Study Inclusion criteria:

- Successful kidney transplantation (KTx) with primary graft function
- Age between 18 and 65 years

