- Control group: patient will be treated according to the standard of care for post-transplant recipients; control patients will be offered the opportunity to undergo the GH regimen for the 1 year after their final visit as a control patient. If the control patients chose to undergo the GH regimen, the extended follow up will be completed after 1 year from their final GH visit (totaling 4 years from the start of intervention).

Long-term follow-up

After the 12 month intervention period all patients will be followed for 2 additional years. Patients will be contacted by phone to assess current activity level, employment status, graft function and current weight. Patient's medical records will also be reviewed to confirm BMI and graft function. This will be done every 6 months.

A separate waiver of documentation of consent, for long-term follow up, is being requested for patients that have previously enrolled and completed the study (January 3, 2012 to July 28, 2014).

Parameters to analyze in all patients:

The PROMIS v.1.1 - Global Health short form will be administered to all patients at the time of enrollment, 6 months and at the end of the study (12 months). The PROMIS v.1.1 - Global Health short form will assesses health in general (i.e. overall health). The PROMIS Global Health short form is a 10-item instrument representing multiple domains (physical function, fatigue, pain, emotional distress, social health) as well as perceptions of general health that cut across domains. Global items allow respondents to weigh together different aspects of health to arrive at a “bottom-line” indicator of their health. Similar global health items have been found predictive of future health care utilization and mortality.

PROMIS 29 Profile v2.0 will be administered to all patients at the time of enrollment, 6 months and at the end of the study (12 months). The PROMIS 29 Prolife v2.0 is a short form containing four items from seven PROMIS domains (Depression, Anxiety, Physical Function, Pain Interference, Fatigue, Sleep Disturbance, and Ability to Participate in Social Roles and Activities) along with a single item on Pain Intensity.

Multiple studies have been conducted by the PROMIS Network validating these instruments. Studies are shown at: <http://www.nihpromis.org/science/validitystudies.aspx>

Body composition and strength

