BMI will be calculated at the time of enrollment, at 6 months, and at the end of the study (12 months). The most exact method to determine body fat and lean body mass is DEXA, a method that has been validated in patients with renal failure before and after transplantation [6,7]. Waist circumference as well as blood pressure will be measured for general health markers. Muscle strength will be measured using a Bidex machine. Exercise capacity will be measure with a 6 minute walk test and an accelerometer. Fitness level will be measure with a maximal aerobic capacity test (VO₂ max). These 7 tests will be done at baseline, 6, and 12 months.

Waist Circumference:

Waist circumference will be measured at the narrowest part of the torso (above the umbilicus and below xiphoid process) in the standing position using a tape measure. This will be completed at baseline, 6 months and 12 months post-intervention.

Blood Pressure:

Blood pressure will be measured in the supine position (lying on back) in a dimly lit room after resting for fifteen minutes. This will be completed at baseline, 6 months and 12 months post-intervention.

DEXA Scan: We will determine percent body fat via a whole body scan by dual energy x-ray absorptiometry (GE, IDX, Madison, WI), which will be operated and calibrated using the manufacturer's stated guidelines. The duration of the scan will be less than 10 min and the subject will be exposed to a radiation dose of ≤ 0.3 mrem based upon the manufacturer's specifications and calculations from Standford Dosimetry, LLC RADAR Medical Procedure Radiation Dose Calculator. This amount of research protocol radiation exposure is minimal given the estimated effective equivalent dose is below the 100 mrem per year, a limit set by the Nuclear Regulatory Commission for "general public" exposure.

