reporting done via the Lifestyle Inventory, understand their eating and sleeping patterns in greater detail by eliminating their opinions and emotional relationship and just focusing on actual intake, and provide a tool for ongoing monitoring and an opportunity for increasing patient's self-reflection on their food and sleeping habits. This will only be administered to the GH patients. Importantly, this is not a measurement tool that we would give at a specific time during the study; it is being used during the study by the research personnel and GH Method personnel to help manage self-reported behavior changes with the patients.

Counseling

Patients in the both arms will be counseled regarding weight loss per standard of care which consists of a pre-transplant and a post-transplant nutrition evaluation and education.

Video recording (optional)

Video recordings will be an option on the consent form for patients that are randomized into the GH exercise group. The option to be video recorded by the GH team at the beginning and end of the patient's 12 months of training. The recordings will be used to compare the progress of the patient from the beginning and end of GH training.

GH Study Visits:

At least one week prior to the first GH session with a patient, the written assessments will be completed and returned to GH personnel for scoring and processing. The first four GH sessions (over 2 weeks) for any patient will be 75 minutes. Following the first 4 sessions, ongoing patients will be slotted into recurring 60 minute time slots for the remaining 50 weeks. All of these visits will occur in the UIC Disability Health and Social Policy Building (DHSP) located at [name] in Suites 158, 190, and 195. The procedure visits at baseline, 6 and 12 months will take 2-3 hours.

At least twice per week, GH personnel will attempt to follow-up with patients via text message, email or a phone call to evaluate their physical recuperation and overall health and energy or to track their performance with a behavior change goal.

Patients will be asked to complete a physical regimen based on the following:

Summary of GH Study Visits:

- Patients may be asked to repeat previous weeks and/or skip a particular week depending on their energy, progress, and overall health.

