
The data will be entered into an Excel spreadsheet and stored on the UIMCC hospital server. The patient data, including age, sex, race, underlying kidney disease, length of hospital stay, rejection episode, comorbidities, and medications will be coded and patient names will not be included in the datasheet.

The de-identified collected data will be entered into a SAS database. Initial descriptive analysis will include calculating means, standard deviations, ranges and frequencies. T-tests for continuous variables and Chi Square or Fischer exact tests of association for

categorical variables will be used to compare results of the study between the two groups for the efficacy parameters listed above. A P value<0.05 will be considered significant.

6) Benefits/risks

The main risk of this research is loss of confidentiality of medical information. Consent will be obtained for all patients. Master patient code list will be kept in a separate file accessible only by the primary investigator. A member of the transplant team will be available to answer any questions or discuss any concerns that patients may have.

The patient may experience mild anxiety or discomfort in providing information about their health and well-being. The patient may also have a potential to feel anxiety when being video recorded (if applicable).

Risks associated with the exercise program

The likely risks and discomforts expected in this study are those that largely involve being engaged in an exercise program after a prolonged period of inactivity. Such risks include: strains, sprains, and muscle soreness. Serious physical injury is considered unlikely given the screening for inclusion and physician approval. We will attempt to reduce risks of injury and harm by promoting gradual increases in exercise across time throughout the 3 month period and having exercise be instructed and supervised by trained professional fitness personnel.

Risks associated with the blood draw:

The risks associated with a blood draw include: mild pain, bleeding or bruising at the site of the draw. In general, any bruising should completely disappear within several days. There are minimal risks of fainting or hypotension (low blood pressure) during or after the blood draw.

Risks associated with the Maximal Aerobic Capacity Test (VO2 Test) and the 6 minute walk test include:

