The risks associated with the treadmill max test and 6 minute walk test include: fatigue, being out of breath, muscle soreness, heart rhythm irregularities, dizziness, loss of consciousness and death. However, serious adverse events (side effects) are very rare and by careful screening and monitoring during the test, the risk of such events are minimized. Further risks include slips, trips, ankle sprains and falls. These risks will be minimized by having a research assistant within arm's reach for stability. All personnel assisting in testing are trained in CPR and emergency lab procedure (including calling 911 and the principal researcher) as outlined by the Department of Kinesiology and Nutrition's procedures and policies.

Risks associated with Vascular Function and Vascular Stiffness measures:

There are no known risks associated with the ultrasound tests used to measure artery stiffness and heart function.. Because we will need to place 3 electrodes on the skin to measure heart rate during these procedures, we may need to shave the area on males where these will be placed which may cause some discomfort and/or redness. Some

adhesive may remain once electrodes are removed which may cause redness. This should wear off within 1-8 hours. For the assessment of endothelial function (FMD), the act of inflating a blood pressure cuff around the arm for five minutes before deflation may cause some discomfort, temporary numbness, or tingling. These discomforts, however generally last for a minimal amount of time post deflation.

Risks associated with the Biodex include

Risks associated with the measure of muscular strength (Biodex) testing include strains, sprains, and muscle soreness, as with an exercise program.

Measures of Physical Activity:

There are no risks associated with the accelerometer. Some other risks include shortness of breath, fatigue and rarely heart attack or stroke, and very rarely death.

Radiation Exposure from the DEXA scan: The duration of the scan will be less than 10 min. The participant will be exposed to a radiation dose of less than or equal to 0.3 mrem based upon manufacturer's specifications and pre-determined calculations. This amount of radiation exposure is minimal given the estimated effective equivalent dose is below 100 mrem per year, a limit set by the Nuclear Regulatory Commission for "general public" exposure.

Risks of Muscle Biopsy and lidocaine use

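### Strains and sprains are named as risks of training and of tests done in both arms, but no record of them is planned in either arm

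*Combined protocol and SAP*

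**What the plan says.** Section 6 (Benefits/risks) lists the expected harms of training: "Such risks include: strains, sprains, and muscle soreness". For strength testing it says: "Risks associated with the measure of muscular strength (Biodex) testing include strains, sprains, and muscle soreness, as with an exercise program". For the treadmill and 6 minute walk tests it adds: "Further risks include slips, trips, ankle sprains and falls". These tests are not confined to the GH arm. Under Body composition and strength, which is part of the parameters for all patients, the protocol says: "These 7 tests will be done at baseline, 6, and 12 months".

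The stated response to injury is prevention and emergency readiness: screening, physician approval, gradual progression, trained supervision, an assistant close by during tests, and staff trained in CPR. Adverse events are mentioned once, in a statement that serious ones are very rare during the exercise tests. The Benefits subsection appoints a physician outside the research to look at outcomes and oversee the study for safety. It does not say what that physician receives, when, or in what form.

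Contact differs by arm. Under GH Study Visits: "At least twice per week, GH personnel will attempt to follow-up with patients via text message, email or a phone call", and "Following the first 4 sessions, ongoing patients will be slotted into recurring 60 minute time slots for the remaining 50 weeks". The control arm has standard of care and the study test visits.

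One related measure is common to both arms: "PROMIS 29 Profile v2.0 will be administered to all patients at the time of enrollment, 6 months and at the end of the study". It includes pain interference and pain intensity.

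**The concern.** The protocol names an expected harm and then plans no way of recording it. A strain or sprain that nobody asks about at the time cannot be reliably recovered at analysis.

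Three features of this design make that matter:

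- The same injuries can come from testing, which both arms undergo. A tally from GH sessions alone cannot separate training from testing.
- Frequent scheduled contact exists only in GH, so whatever is noticed informally will come mostly from that arm.
- Controls are offered the GH regimen after their final control visit, so injury experience in the first year bears on a decision made within the trial.

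**Working it through.** The plan states no injury figure, so there is none to reproduce. The check is a search of the text, then arithmetic on the contact schedule and on precision.

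**1. Places where an injury record could sit**

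- Parameters to analyze in all patients: questionnaires, body composition, strength, blood, vascular and cardiac measures. No injury item.
- Long-term follow-up calls: activity, employment, graft function and weight. No injury item.
- Coded patient data in section 5: an open list that names no injury field.
- Between-group tests in section 5: the five efficacy criteria only.
- Visit schedule table: ten rows, none for injuries.
- PROMIS-29: pain scores in both arms. These may reflect soreness, but they do not show whether an injury occurred.

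**2. Scheduled study contacts after baseline, per patient over 12 months**

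- GH sessions: 4 + 50 × 2 = 104.
- GH follow-up attempts: at least 2 × 52 = 104, taking the twice-weekly attempts to run for all 52 weeks.
- Test visits: 2 in each arm. For control these are the only scheduled study contacts stated. The frequency of routine clinic contact is not given.

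**3. Effect of unequal contact on an informal count**

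If a share p is truly injured in both arms, and informal capture is g in GH and c in control, the apparent excess is p × (g − c). None of these inputs is in the documents. Assuming p from 5% to 20%, g = 90% and c from 70% down to 30%, the excess runs from 0.05 × (0.9 − 0.7) = 1 point to 0.20 × (0.9 − 0.3) = 12 points. The direction follows from the contact schedule. The size is only the assumed capture rates restated.

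**4. Why the question must also reach people who stop**

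Assume true injury of 20% in GH and 10% in control, with a tenth of everyone other than injured GH patients missing the visit.

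- 40% of injured GH patients miss it: 0.20 × 0.60 / (0.20 × 0.60 + 0.80 × 0.90) = 0.12 / 0.84 = 14.3%.
- 60% miss it: 0.08 / (0.08 + 0.72) = 10.0%.
- Control: 0.09 / (0.09 + 0.81) = 10.0%.

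A true excess of 10 points would shrink to 4.3 points, or to nothing.

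**5. Precision with a common question at 180 v 45**

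Exact unconditional 95% intervals for GH minus control, in percentage points, with near-equal rates:

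- About 5% injured: 9 v 2 events, −10.8 to 6.4; 9 v 3 events, −13.7 to 4.9. Half-widths 8.6 and 9.3.
- About 10%: 18 v 4, −12.1 to 9.1; 18 v 5, −14.9 to 7.7. Half-widths 10.6 and 11.3.
- 20%: 36 v 9, −15.4 to 11.8. Half-width 13.6.

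With 20% lost (144 v 36, an assumption) the half-widths are 9.4–10.5, 11.8–12.5 and 15.3–15.6. Two-sided Fisher power at 0.05 (GH v control) is 10% for 10% v 5%, 30% for 20% v 10%, and 73% for 20% v 5%.

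**The case against.** **The record may exist elsewhere.** The visit schedule is an incomplete summary: it also omits VO₂ max, waist circumference and cardiac ultrasound, which the text plans at the same visits. The coded-data list is open. The consent pages were not available, nor were the departmental procedures cited for test emergencies. This stands as a caution, and absence from the schedule alone would prove little. The point rests on the whole protocol text, which has no injury item in any of the places listed above.

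**No injury comparison is planned, so none can be biased.** This stands too. A reader might infer that the trial will report a false injury excess in GH, perhaps by a stated ratio. The documents do not support that. Section 5 confines its tests to efficacy, any ratio would come only from assumed capture rates, and unequal capture of this kind would overstate GH harm and not hide it.

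**The physician may receive injury information anyway.** A reader might infer that the physician would have no such information. The documents show only that no injury input is specified. Records or staff reports could reach that person informally.

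**The yield is low.** Serious injury is expected to be unlikely, soreness is partly covered by PROMIS pain, and only a large excess would be detected. That argues for estimating and not testing. It does not argue against asking.

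**Conclusion.** The gap holds in a limited form. Strains and sprains are named for training and for tests in both arms, no record of them is planned in either arm, and no injury input is defined for the safety physician. Informal capture would be unequal because frequent scheduled study contact exists only in GH, but the documents do not allow the inequality to be sized. The five efficacy comparisons are untouched. This is a cheap improvement for patient safety and balanced reporting, not a threat to the trial's main results. The verdict assumes that no injury form exists in material outside these documents. The precision figures rest on assumed injury rates of 5% to 20%.

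**What to change.** Add an injury row to the visit schedule. At the existing 6- and 12-month visits, have the staff who already run the test visits ask both arms one identical question: any strain, sprain, fall or other injury since the last visit, whatever the cause, and whether it needed care or stopped usual activity. Ask it by phone or at exit for anyone who stops or misses a visit. Log injuries that happen during the baseline, 6- and 12-month test visits separately, in both arms. List events known only from GH sessions or contacts apart, and do not compare them with control.

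In section 5, add a descriptive table by randomised arm with confidence intervals and no significance claim, and state that it goes to the safety physician. The choice of interval method can be left to the trial statistician.

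Cost: about 225 × 2 = 450 answers, with a phone or exit answer standing in for a missed visit; at most 225 × 3 = 675 log lines; and one table.

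Downsides to state beside the table: six-month recall; patients know their arm, so GH patients may report more readily; low precision; and injuries from the 12-month tests that appear after the visit are still missed.
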